8.4.1 Criteria for Early Termination

A subject may withdraw or be withdrawn from the study for the following reason.

- Subject withdrew consent.
- Sponsor requested subject to be withdrawn.
- Request of primary care physician or investigator.
- Protocol violation/ Non-compliance.
- Lost to follow-up/failure to return.
- Adverse Event (specify primary AE in the AE log).
- Marked disease progression as defined at any time during study drug therapy.
- The occurrence of marked progressive liver disease
- Unresolved or recurrent grade III or IV toxicity.
- Pregnancy.
- Death.
- Other.

8.5 Temporary Discontinuation of Study Drug Treatment

Temporary discontinuation is defined as missing more than three consecutive doses. The reasons for temporary IMP/study drug discontinuation should be recorded in the subject source document and the study drug administration and interruption eCRF pages and the local clinical management should be notified. The subject will report any temporary discontinuation to the investigator and will be instructed by the investigator regarding continuation of treatment.

8.6 Investigational Medicinal Products/Study Drugs

8.6.1 Treatments Administration

Subjects will be administered Aramchol as follows:

- One tablet of Aramchol 400 mg and one tablet of matching placebo for Aramchol.
- One tablet of Aramchol 400 mg and one tablet of Aramchol 200 mg.
- Two tablet of Aramchol matching placebo.

The tablets should be taken orally in the morning within 30 minutes after breakfast with a glass of water (250 ml).

Subjects are allowed to omit study drugs up to 3 consecutive days during the study.

8.6.2 Method of Assigning Subjects to Treatment Groups

There will be a screening period of 4 weeks (with an option to extend it up to 45 days), during which the subject will be assigned a screening number through the Interactive Web Response System (IWRS). At the baseline visit, subjects who are deemed eligible will be assigned to one of three possible treatment groups by the IWRS according to the randomization scheme produced by the CRO's statistician on behalf of Galmed Pharmaceutical Ltd. Each subject will be allocated a unique randomization number in addition to their screening number. The IWRS will keep track of subjects' visits and status.

A randomization list will be generated prior to the study initiation, using a computerized algorithm. The randomization will be performed in blocks, 48 blocks containing 5 subjects each in a 2:2:1 ratio (2 subjects for each of the active groups and 1 placebo).

8.6.3 Blinding

The investigators, the sponsor and any personnel involved in subjects' assessments, monitoring, analysis and data management (excluding the designated Clinical Supplies Unit's personnel), are blinded to the subject assignment.

8.6.4 Emergency Code Breaking

In case of a serious adverse event or pregnancy, when the study drug assignment is needed to make treatment decisions for the subject, the investigator may unblind the subject's drug assignment. The sponsor should be notified of the event prior to breaking the code, if possible. If this is not possible, the sponsor should be notified immediately afterwards, and the subject's drug code assignment should not be revealed. The circumstances leading to the breaking of the code should be fully documented, in the investigator's study files and in the subject's source

documentation. Treatment assignment should not be recorded in any study documents or source document.

In studies conducted in the EU for AEs that are defined as: Suspected, Unexpected, Serious, Adverse Reaction (SUSAR), the Global Drug Safety & Pharmacovigilance (GDSP) may break the subject's code for possible regulatory submission.

8.6.5 Description of Investigational Medicinal Products/Study Drugs

Aramchol tablets 200 mg, 400 mg and placebo for Aramchol tablets are manufactured in compliance with current Good Manufacturing Practice (GMP) standards and guidelines applicable to IMPs

. The color of Aramchol 200 mg, 400 mg and their matching placebo tablets are of identical appearance, gray non-coated tablets, to maintain study blinding. Aramchol 200 mg and its matching placebo are round and Aramchol 400 mg and its matching placebo are oval.

8.6.6 Packaging and Labeling

The study drugs are packaged in HDPE 100ML Duma Twist Off containers. Each container will contain 35 tablets. Each kit will contain 2 bottles. The bottles are capped with PP Duma Twist off Caps.

The label on the bottles will include a fixed information (i.e. product name, dosage, storage conditions, instructions etc.) and the kit number.

Each patient monthly kit will include 2 bottles. The label on the kit will include fixed information (i.e. product name, dosage, storage conditions, instructions etc.) and a variable information section. The variable information section will include 2 parts: 1 detachable label, which will be attached to the subject's file upon bottle dispensing and 1 label to remain on the bottle. The variable information section will include the following variable data: batch code, bottle number, and expiration date (all to be pre-printed) and blank fields for investigator name, visit number and subject number. These blank fields will be manually filled-in by the Investigator or designee upon provision of the kit to the subject.

8.6.7 Distribution and Shipment

A sub-contracted Vendor, according to the distribution guidelines, will perform distribution and shipment of IMP.

The IMP bottles will be packed and shipped at room temperature in appropriate storage boxes. If the IMP supplies appear to be damaged/missing upon arrival at the investigational site, the sponsor should be contacted immediately.

Each shipment of IMP supplies for the study will contain a shipment form describing the content of the shipment. This form will assist the site in maintaining current and accurate inventory records. When a shipment is received, the site investigator/

When a shipment is received at a depot, acknowledgement of receipt of the IMP supply will be coordinated by the sending center.

Importing of the IMP by an EU member will be carried out according to the provisions of Directive 2001/20/EC, Article 13. Importing to any other participating country will be done according to the local regulations.

8.6.8 Storage, Dispensing and Return

IMP supplies will be kept in a secure, limited-access, temperature-controlled storage area .

Only authorized personnel will have access to the IMP. The study site personnel at each site will be responsible for correct storage and handling of the IMP.

All IMP bottles must be stored at room temperature.

The IMP kits will be dispensed to the subject at the study site at visits 2, 4 - 9 & unscheduled visits (as needed). The bottles will be assigned to subjects according to the randomization list provided by the CRO. At dispensing visits, the site personnel should fill in the subject's number, the visit number and the Investigator's name on the label of the dispensed bottle as well as on the detachable label, which is adhered to the subject's file.

At each visit during the treatment period the subject will receive 1 - 3 kits of IMP according to the period between the visits. The dispensed total should include an amount that will suffice until the following scheduled dispensing visit. The subject should finish all of the tablets in each kit before moving to the next kit.

Subjects will be instructed to store IMP at room-temperature and to return all used empty bottles and unused IMP at each visit. The site investigator/site coordinator is responsible for performing IMP accountability at the site. The monitor is responsible for the accountability of the returned IMPs.

8.6.9 Verification of Compliance with Treatment Regimen

At each study visit, the investigator/site coordinator will assess the subject's compliance with the prescribed regimen for the study medication. This will include checks of protocol

compliance and use of study drug in order to assess the reliability of subject-generated data. Subjects who fail to comply with the study requirements may be withdrawn from the study, following consultation with the sponsor.

Compliance with the dosing regimen will be determined by performing IMP accountability of returned bottles of the IMP used and unused at each visit. Site personnel will record the number of used, unused and lost tablets on the Accountability Log. Percent compliance will be calculated as the number of used capsules divided by the number of total capsules expected to be used, multiplied by 100. Subjects with less than 75% compliance between previous visit to the clinic and the current one will be warned. If a second incident of non-compliance occurs, the subject will be withdrawn from the study.

8.6.10 Accountability and Compliance

IMP accountability records must be maintained at the site at all times.

Upon Galmed's (or Galmed's designee) monitor visit at the site, accountability of the returned IMPs should be performed and recorded by the monitor. The subject number, the date, batch code, bottle (kit) number and quantity of IMP returned by the subject will be checked for correctness and recorded on the appropriate accountability form.

At the end of the study, the monitor must return all IMP (used and unused bottles) and the corresponding accountability forms to the sponsor or sponsor's designee (CRO) for reconciliation and destruction. A photocopy of these records must be kept at the study sites. If needed, IMP can be returned during the study upon sponsor approval.

9 ASSESSMENTS METHODS

9.1 NMRS evaluation

All subjects will have two NMRS evaluations at the beginning of the study (Visit 1) and at visit 10 (Early Termination/End-of-Treatment). The End-of Treatment NMRS should occur 0 - 7 days prior to visit 10, before the subject stops taking study medication or within 7 days after the visit. For patients that early terminated from the study, MRI will be recommended to patients that completed at least 24 weeks in the study (visit 7).

All subjects should maintain a low fat high carbohydrate iso-caloric diet within 48 hours prior to MRI scan. Any alcohol consumption is not allowed during this period. Fasting for 6 hours before the MR scan is required (only water allowed).

All NMRS scans will be evaluated locally for any clinical abnormalities. The clinical report should be forwarded to the investigator within 48-72 hours. If abnormalities are found during the screening NMRS, it is up to the investigator's discretion whether to include the patient in the study, to include him after further exploration the findings or exclude the patient.

The primary efficacy parameter to be assessed will be liver triglyceride concentration: Liverfat/water ratio in the liver. This will be evaluated in the MRI unit at Tel Aviv Sourasky Medical Center (Appendix A) who will act as a central reading center.

9.2 Liver Biopsy

Biopsies will be performed at the screening visit (if not performed within 6 months prior) and at visit 10 (End-of Treatment/Early Termination. The End-of-Treatment biopsy should occur 0 - 7 days prior to visit 10, before subject stops taking study medication or within 7 days after it. For patients that early terminated from the study, biopsy will be recommended to patients that completed at least 40 weeks in the study (visit 9).

Coagulation results should be within normal ranges before biopsies are performed. Coagulation values outside the normal range should be evaluated by the Investigator to determine subject eligibility and the scheduling/timing of the biopsy. If the subject is taking any anti-coagulant drug, it should be stopped or specifically antagonized in sufficient time before biopsy is taken. Investigators should take into account the pharmacokinetic properties (e.g., half-life) of the anti-coagulant or antagonist drug to allow sufficient time for desired effect. Taking NSAIDs should be prohibited 48 hours prior to conducting biopsy.

Slides will be prepared at each site (Appendix B) and will be sent to the Institute of Pathology, Medical University of Graz [name] for evaluation. This center will act as the central reading center for the study.

Liver biopsy may be recommended for definitive diagnosis of any rapidly progressive liver disease or unusual phenomena which may be suspicious of alteration in the disease, or suspicious for another disease affecting the liver.

9.3 NAFLD Fibrosis Score (NFS):

The score will be calculated for based on the following formula: -1.675+0.037Xage (years) + 0.094xBMI (kg/m2) + 1.13XIFG/diabetes (yes=1, no=0) +0.99XAST/ALT ratio - 0.013Xplatelet(x109/l) - 0.66Xalbumin (g/l)

9.4 HOMA

The Homeostasis Model Assessment (HOMA) estimates steady state beta cell function (%B) and insulin sensitivity (%S), as percentages of a normal reference population. These measures correspond well, but are not necessarily equivalent, to non-steady state estimates of beta cell function and insulin sensitivity.

This parameter will be calculated based on plasma glucose level and insulin, which will be tested among other lab tests .

HOMA –IR calculation: [glucose (mmol/L)*insulin (μ U/mL)/22.5], using fasting values. HOMA-Beta = 20*[Insulin(μ U/mL)] / ([Glucose mmol/L] – 3.5) %,.

9.5 Fatty liver Index (FLI)

Fatty Liver Index will calculated by the following equation (24):

 $FLI = (e \ 0.953*loge \ (triglycerides) + 0.139*BMI + 0.718*loge \ (ggt) + 0.053*waist circumference - 15.745) / (1 + e \ 0.953*loge \ (triglycerides) + 0.139*BMI + 0.718*loge \ (ggt) + 0.053*waist circumference - 15.745) * 100$

9.6 Blood Metabolomics

The assessment will be done on week -4 (screening visit), visit 7 and week 52 (End-of-Treatment/Early Termination) visit will be collected from all patients.

Small part of the liver biopsy will be collected from about 15 consenting patients (the same patients) during the screening and the termination visits.

Serum samples as well as biopsy samples will be prepared and stored as described in Appendix C. Samples will be analyzed at OWL (One Way Liver Genomics, S.L.), [name].

9.7 Endothelial Function

The assessment will be done during the baseline visit before first dose is taken and at visit 10 (End-of Treatment/Early Termination visit) This test will be conducted at selected sites. If the Endothelial Function test was not done on Visit 2 (Day 0) or needs to be repeated due to unacceptable test data, it will be done at Visit 3 (two weeks after Visit 2) – or at an Unscheduled Visit before Visit 3.

The examination will be conducted as describe in Appendix D. The data collected will be analyzed by Itamar Medical Ltd. [name].

9.8 Aramchol blood trough level

Blood samples for trough Aramchol blood level will be collected from subjects participating in the study in Israel at visits 2 (baseline), 4, 6, 7, 9, 10 and 11.

One blood sample will be collected on visit 4 or 9 at selected sites in Mexico, USA, Europe and Hong Kong to test for trough Aramchol blood level differences between populations (e.g., African American, Asian, Hispanic).

In these visits the subjects will be asked not to take the study medication before attending the visit at the clinic but only after the blood sample for trough Aramchol blood level will be taken. The date and time of the blood sample, as well as the date and time of the last study drug dose prior to the sample will be recorded on the e-CRF.

The blood samples will be collected and transferred into pre-labeled pre-chilled (ice-based water bath (4^oC)) EDTA-K2 tubes. Following each collection, the tube will be gently inverted several times to assure complete mixing with the potassium EDTA and should then be placed on ice pending centrifugation.

Plasma will be separated by centrifugation for 10 min within 45 minutes of collection at approximately 2000g (2600-3000 rpm) and +4°C. Deviations from the blood sampling times will be recorded in the appropriate eCRF. Plasma samples will be divided into duplicate labeled Cryotubes (at least 600 μ l per tube) by the site and sent frozen on dry ice to the central laboratory for storage at -70°C. Samples for blood trough levels evaluation will be sent periodically on dry ice to Analyst Research Laboratories, Rehovot, Israel. All shipments will be accompanied by a detailed sample inventory list, and the bio-analytical laboratory will be notified in advance by telephone, fax or e-mail before the shipment of study samples. Aramchol plasma concentrations will be determined using a validated LC-MS/MS method.

9.9 Changes in Lifestyle

The subjects will be counselled on the importance of diet and exercise in proper weight management and asked if any change took place in their lifestyle between visits to the clinic. These changes can be in:

- Their diet (meal composition or what they are eating).
- Their physical exercise.

Life style Questionnaire (appendix E) may be used as a guideline, but is not mandatory.

For each sample, it is required 7cc K3-EDTA frozen whole blood. Appropriate tubes will be provided by the CRL. The samples can be stored in a -20°-80° freezer. The samples of all patients will be stored at CRL and from time to time will be sent to the examining Lab.

The unutilized genetic material will be destroyed at the central lab and a destruction certificate will be issued.

10 SAFETY ASSESSMENTS

10.1 Adverse Events

Adverse events will be recorded from when a subject has signed the Informed Consent Form and throughout the study, including the follow-up period. They should be reviewed and updated at each subsequent visit and during any phone contact with the subject.

10.2 Safety Laboratory Evaluations

All laboratory testing will be performed by a central laboratory facility and/or affiliated laboratories which work under the central laboratory regulations and within its tests normal ranges. On visits 3, 4, 5 and 9 those tests can be performed at site's local lab or at a central lab. The lab manual should be referred to for specific instructions.

The following tests will be performed:

- Serum Chemistry
 - Fasting Plasma Glucose
 - Creatinine
 - Creatinine Clearance
 - Bilirubin (direct and total)
 - Urea
 - AST (SGOT)
 - ALT (SGPT)
 - GammaGT (GGT)
 - Lipid profile- once in the study either at screening or any other visit; 8-12 hours fasting is mandatory: Total cholesterol, LDL cholesterol, HDL cholesterol, VLDL and triglycerides.
 - Albumin
 - CPK
 - Alkaline Phosphatase
 - hs-CRP
- Electrolytes
 - Sodium
 - Potassium

Protocol No: 005 ARREST study

- Chloride
- Calcium
- Phosphorous
- Coagulation
 - Fibrinogen
 - PT/INR
 - aPTT
- Serology (only at screening)
 - HBV
 - HCV
 - HIV
- Hematology
 - Hemoglobin
 - MCV
 - Hematocrit
 - Red Blood Cells count (RBC)
 - White Blood Cells count + differential
 - Platelet count
 - Basophils
 - Eosinophils
 - Lymphocytes
 - Monocytes
 - Neutrophils
 - Large Unstained Cells
- Urinalysis
 - pH
 - Blood
 - Glucose
 - Ketones
 - Erythrocytes
 - Protein
 - Specific Gravity (USG)
 - Nitrite
 - Leukocytes
 - Bilirubin
 - Urobilinogen
- ESR

Measurement of Complete Blood Counts, INR and chemistry are in fact regarded as current clinical practice for fatty liver patients, and should therefore be collected and analysis performed by the Central Laboratory according to the Visit Schedules.

The sponsor must be provided with a copy of the laboratory's certification, and a tabulation of the normal ranges for each parameter required. Additionally, if at any time a patient has laboratory parameters obtained from a different outside laboratory, the sponsor must be provided with a copy of the certification and a tabulation of the normal ranges for that laboratory. At any time during the study, abnormal laboratory parameters which are clinically relevant (e.g. require dose modification and/or interruption of study drug, lead to clinical symptoms or signs or require therapeutic intervention), whether specifically requested in the protocol or not, must be recorded on the appropriate Comment CRF page in addition to the appropriate laboratory CRF page. When abnormal laboratory values or test results constitute an adverse event (i.e., induces clinical signs/ symptoms or requires therapy) they must be recorded on the Adverse Events CRF.

When, in the opinion of the investigator, other clinical laboratory evaluations may be relevant for assessing the patient's status, they will be completed and entered into the database as appropriate.

Special tests:

- Total cholesterol, HDL cholesterol, LDL cholesterol and triglycerides will be specifically determined as probable safety parameters in this study, which affect lipid metabolism.
- See Section 9.11 for additional specialty test (Exploratory Laboratory tests and other Laboratory tests needed)

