	The subjects will be evaluated at study sites for 11 scheduled visits: at screening (visit 1(weeks $-4 - 0$)), baseline (visit 2 (day 0)), visit 3 (week 2), visit 4 (week 4), visit 5 (week 8), visit 6 (week 12), visit 7 (week 24), visit 8 (week 32), visit 9 (week 40) and visit 10 (week 52 End-of-Treatment/Early Termination visit). After completion of the study treatment period, the subjects will be followed for an additional period of 13 weeks without study medication until visit 11 (week 65).
	 During the screening period, the severity of the disease will be evaluated with blood tests, liver biopsy and NMRS. During the study the following assessments will be performed: Vital signs will be measured at each study visit. A physical examination will be performed at the screening visit, 24 weeks, End-of-Treatment/Early Termination and week 65 visit. The following blood tests will be performed: complete blood count (CBC), serum chemistry (including electrolytes, liver enzymes, direct and total bilirubin, glucose, lipid profile which include triglyceride, cholesterol, HDL, LDL and VLDL, CPK, creatinine, urea, albumin, alkaline phosphatase), ESR and urinalysis during the screening visit, baseline, week 2, 4, 8, 24, 40, 52 and 65 (end of follow up) visits. Serology (HBV, HCV and HIV) will be performed during the screening visit. Coagulation (fibrinogen, PT/INR, aPTT) will be measured at screening and baseline, week 24 and End-of-Treatment/Early Termination visits. HbA1C will be measured at the screening, week 8, 24, 40 and End-of-Treatment/Early Termination visits. C reactive protein, Leptin, Adiponectin,
	will be measured at the baseline visit and end of treatment period. The blood samples taken at these visits, will be tested for possible biomarkers. TSH, T3 and T4 will be measured during the screening visit. β -hCG in women of childbearing potential will be performed during the screening visit. A serum sample will be collected and kept frozen until study end in case special investigation needs to be performed. This sample will be collected during the screening and visit 10/Early Termination.

	- Body weight and waist circumference will be measured at
	screening, baseline, week 24, end of treatment and week 65 visits.
	Height will be measured during the screening visit.
	- ECG will be performed during the screening visit, visit 7 (week 24)
	and End of Treatment/Early Termination visit.
	- All subjects will undergo two NMRS scans, at screening and end of

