5 STUDY DESIGN

5.1 Over view and plan

This is a multicenter, phase IIb, randomized, double blind, placebo controlled study designed to evaluate the efficacy and safety of two Aramchol doses (400 mg and 600 mg) in subjects that

are 18 to 75 years of age, with Non-Alcoholic Steatohepatitis (NASH) and type II DM or elevated fasting glucose and overweight/obesity (type II diabetic or pre diabetic). Eligible subjects will be enrolled in three treatments arms:

- Aramchol 400 mg tablets
- Aramchol 600 mg tablets
- Placebo for Aramchol

The subjects will be evaluated at study sites for 11 scheduled visits: visit 1 (screening), visit 2 (baseline), visit 3 (2 weeks), visit 4 (4 weeks), visit 5 (8 weeks), visit 6 (12 weeks), visit 7 (24 weeks), visit 8 (32 weeks), visit 9 (40 weeks), visit 10 (End-of-Treatment/Early Termination) (52 weeks) and visit 11 (follow up) (65 weeks).

The subjects will be treated for a period of 52 weeks. After completion of the study treatment period, the subjects will be followed up for an additional period of 13 weeks without study medication

During the study the following assessments will be performed:

- Vital signs will be measured at each study visit.
- A physical examination will be performed at the screening visit, 24 weeks, End-of-Treatment/Early Termination and week 65 visits.
- The following safety blood tests will be performed: complete blood count (CBC), serum chemistry (including electrolytes, liver enzymes, direct and total bilirubin, glucose, lipid profile which include triglyceride, cholesterol, HDL, LDL and VLDL, CPK, creatinine, urea, albumin, alkaline phosphatase), ESR and during the screening visit, baseline, week 2, 4, 8, 24, 40, 52 and 65 (end of follow up) visits. Serology (HBV, HCV and HIV) and urinalysis will be performed during the screening visit. Coagulation (fibrinogen, PT/INR, aPTT) will be performed during the screening, baseline, week 24, End-of-Treatment/Early Termination and week 65 visits. Insulin (HOMA) will be measured in the screening, week 24 and End-of-Treatment/Early Termination visits. HbA1c will be measured in the screening, week 8, 24, 40 and End-of-Treatment/Early Termination visits. C reactive protein, Leptin, Adiponectin,

will be measured in baseline visit and end of treatment period (week 52, visit 10). The blood samples taken at these visits, will be tested for possible biomarkers

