The difference in changes from baseline to end of study between the study groups will be analyzed using ANCOVA with adjustment for baseline measurement for the following secondary and exploratory endpoints:

- Change in ALT levels.
- Change in insulin resistance, measured by HOMA score.
- Change in A1CHbA1c levels
- Change in Adiponectin level and Leptin: Adiponectin ratio (LAR).
- Change in inflammation and fibrosis biomarkers: Fibrinogen, CK-18, hs-C-reactive protein (hs-CRP), TNFα, IL-6 and fibrosis tests (NFS).
- Change in body weight and in waist circumference.
- Changes in fatty liver index (FLI)

Additional exploratory endpoints (e.g. Metabolomics and Genetic profiling) will be summarized in appropriate tables by study group.

Safety Analysis:

- 1. Adverse events and serious adverse events
- 2. Safety laboratory evaluations.
- 3. Vitals signs.
- 4. 12-Lead ECG
- 5. Physical examinations
- 6. Drop-out rates

Interim Safety Analysis:

An independent DSMB will analyze the safety data collected during the first 6 months for the 120 subjects and recommend a continued course of action. All patients will continue to be treated under the study protocol as done during the 6 months prior the cutoff date, till conclusion of the analysis will be known.

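### Section 10.2 limits the lipid profile to one measurement per subject, against nine in the synopsis and Section 5.1; followed literally, lipid change from baseline and FLI change cannot be computed

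*Combined protocol and SAP*

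**What the plan says.** Section 10.2 itemises the serum chemistry panel. Its lipid entry, covering total, LDL and HDL cholesterol, VLDL and triglycerides, carries a limit that no other chemistry item has: "Lipid profile- once in the study either at screening or any other visit", with a fast of 8 to 12 hours required.

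The synopsis describes serum chemistry as including electrolytes, liver enzymes and a "lipid profile which include triglyceride, cholesterol, HDL, LDL and VLDL", and attaches one schedule to the whole group of blood tests: "ESR and urinalysis during the screening visit, baseline, week 2, 4, 8, 24, 40, 52 and 65 (end of follow up) visits". Section 5.1 repeats the panel and the visits: "ESR and during the screening visit, baseline, week 2, 4, 8, 24, 40, 52 and 65 (end of follow up) visits".

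Section 10.2 closes its test list by saying that blood counts, INR and chemistry "should therefore be collected and analysis performed by the Central Laboratory according to the Visit Schedules". Under special tests, the same section singles lipids out because the study affects lipid metabolism: cholesterol fractions and "triglycerides will be specifically determined as probable safety parameters in this study".

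Three parts of the plan use the lipid values:

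- Section 12.9.2 plans summaries of every quantitative laboratory parameter and its change from baseline, by scheduled visit and treatment group. It also plans a table of potentially clinically significant (PCS) values, in which cholesterol is flagged above 7.75 mmol/l and only post-randomization measurements count.
- Section 9.5 defines FLI from triglycerides, BMI, GGT and waist circumference. Sections 8.2.3 and 8.2.6 list FLI at Visit 2 and Visit 10.
- Section 12.11 lists "Changes in fatty liver index (FLI") among the changes from baseline to end of study to be analysed by ANCOVA.

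**The concern.** The protocol gives two incompatible collection rules for the same panel, and the rest of the visible text does not say which one governs. The visit-by-visit instructions in Section 8.2 order chemistry without listing its contents. A site or laboratory that looks up the contents in Section 10.2 meets the once-only limit.

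One value per subject supports a cross-sectional description and nothing longitudinal. The lipid safety evaluation in Section 12.9.2 and the change in FLI both need a value before treatment and another after it. If sites resolve the conflict differently, lipid data will be complete at some and a single value at others, for parameters that the protocol itself names as safety parameters.

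**Working it through.** No sample size, power or alpha enters this point, and the plan states no figure to reproduce. The check is a count of time points, followed by a test of which planned quantities a single draw can support.

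**Step 1: count the scheduled draws.**

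| Source | Lipid time points | Count |
|---|---|---|
| Synopsis | screening, baseline, weeks 2, 4, 8, 24, 40, 52, 65 | 9 |
| Section 5.1 | the same | 9 |
| Section 10.2, lipid line | one, at any visit | 1 |
| Section 10.2, closing statement | chemistry per the visit schedules | as scheduled |

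Of the nine, 9 − 2 = 7 come after baseline.

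Nine is the number of draws, not the number of central-laboratory values. Section 10.2 and a Table 1 footnote allow Visits 3, 4, 5 and 9 (weeks 2, 4, 8 and 40) to be analysed locally, while Section 12.9.2 analyses central-laboratory data. At a site using a local laboratory for all four visits, 9 − 4 = 5 central values remain: screening, baseline and weeks 24, 52 and 65. The contrast is then one against five.

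**Step 2: take each possible timing of a single draw.** A change from baseline is Δ = Y(post) − Y(baseline) and needs two values. FLI (Section 9.5) is 100·e^y/(1 + e^y), with y = 0.953·ln(triglycerides) + 0.139·BMI + 0.718·ln(GGT) + 0.053·waist − 15.745. It therefore needs a triglyceride value at each visit where it is calculated.

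| Single draw at | Lipid change | FLI at Visit 2 | FLI at Week 52 | FLI change | Post-randomization cholesterol for PCS table |
|---|---|---|---|---|---|
| Screening | no | only if carried to Visit 2 | no | no | no |
| Baseline | no | yes | no | no | no |
| Week 2, 4, 8, 24, 40 or 65 | no | no | no | no | yes |
| Week 52 | no | no | yes | no | yes |

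Lipid change and FLI change are each available under 0 of 9 timings. Week 52 FLI is available under 1 of 9, and FLI at Visit 2 under at most 2 of 9. The PCS table loses the subject under 2 of 9. These are counts of timings, not probabilities; nothing in the protocol says how sites would choose.

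**Step 3: could one triglyceride value serve both ends?** Carrying it across would remove the triglyceride contribution from the change. A 20% fall in triglycerides shifts y by 0.953·ln(0.8) = −0.213, and a halving by 0.953·ln(0.5) = −0.661. Section 9.5 gives no units, so mg/dl, U/l and cm are assumed here. For an illustrative subject with BMI 27, waist 95 and GGT 30, triglycerides of 300 and 150 give FLI of 71.5 and 56.5. With BMI 33, waist 108 and GGT 50, they give 94.3 and 89.6. The omitted part can be appreciable, so carrying a value across is no substitute for a second measurement.

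**Step 4: apply the synopsis and Section 5.1 schedule instead.** Lipids are then drawn at baseline and at Week 52, and every quantity in the table can be computed.

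**The case against.** The strongest reply is that a site would have to follow one sub-item of Section 10.2 over most of the protocol. Section 8.1 says assessments follow Table 1, Section 8.2 orders chemistry at the relevant visits, and the synopsis and Section 5.1 define chemistry as including lipids. FLI at Visits 2 and 10 implies triglycerides there. Section 10.2 also points to a laboratory manual, not among these documents, which may settle the panel. This stands as a limit on how likely the loss is. It does not remove the contradiction.

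The line might be read as asking for only one fasting lipid sample. It does not say that, and Section 8.2 already asks for 8 to 12 hours' fasting at visits with laboratory draws.

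Several stronger readings are tempting but unsupported:

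- *Week 52 FLI becomes impossible.* A reader might infer this, but the line permits any visit, and a Week 52 draw would give that value. It is the change that is lost.
- *The data would be irrecoverable.* Serum is frozen at screening and Visit 10 (Sections 8.2.1 and 8.2.6), with metabolomics serum also stored from screening, Visit 7 and Visit 10 (Section 9.6, Appendix C). Partial rescue is conceivable, although no lipid re-assay is planned and most intermediate visits would stay empty.
- *Table 1 confirms that lipids are left out.* A blood chemistry row is legible and a lipid row is not, but the table is too damaged in the available text for absence to prove anything.
- *A formal FLI endpoint is defeated.* The FLI-change line stands in Section 12.11 beside Dunnett, ANCOVA and ITT text that conflicts with Sections 12.5 to 12.7, and the SAP prevails. The current status of that analysis is uncertain. The collection of FLI at Visits 2 and 10 is not.

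**Conclusion.** The contradiction is real: one lipid measurement in Section 10.2 against nine in the synopsis and Section 5.1, with Section 10.2 also at odds with its own closing statement on chemistry.

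The size is conditional. For a subject handled under the once-only line, lipid change from baseline and FLI change are unavailable whatever the timing, and a screening or baseline draw also removes that subject from the cholesterol PCS table. For a subject handled under the synopsis and Section 5.1, nothing is lost. The documents do not show that any site follows the once-only line, so no overall proportion of missing data can be given.

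The conclusion assumes that the line means what it says and that the laboratory manual does not override it. It concerns lipid safety summaries and FLI. The NMRS primary endpoint and the five key secondary endpoints do not use lipids and are unaffected. Because the affected values are named safety parameters and the correction is nearly free, it should be made.

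**What to change.** Reconcile the passages. In Section 10.2, replace the once-only wording on the lipid line with a reference to the chemistry visit schedule in the synopsis and Section 5.1, keeping the fasting requirement. State in Table 1, by footnote, that blood chemistry includes the lipid profile, so that triglycerides are available at Visits 2 and 10, where FLI is already scheduled. Check that the laboratory manual agrees.

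The cost is a wording change and lipid assays on blood already drawn. No visit or blood draw is added.
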